#### ANNEX 6: Definitions of Severe Malaria

**Impaired consciousness:** A Glasgow Coma Score <11 in adults or Blantyre coma score <3 in children

**Acidosis:** A base deficit of >8 meq/l or, if unavailable, a plasma bicarbonate of <15 mM or venous plasma lactate >5mM. Severe acidosis manifests clinically as **respiratory distress** – rapid, deep and laboured breathing

**Hypoglycaemia:** Blood or plasma glucose <2.2mM (<40mg/dl)

**Severe malarial anaemia:** A haemoglobin concentration <5g/dl or a hematocrit of <15% in children <12 years of age (<7g/dl and <20%, respectively, in adults) together with parasite count of > 10,000  $\mu$ /l

**Renal impairment (acute kidney injury):** Plasma or serum creatinine >265  $\mu$ M (3 mg/dl) or blood urea >20 mM

**Jaundice:** Plasma or serum bilirubin >50  $\mu$ M (3 mg/dl) together with a parasite count >100,000  $\mu$ /l

**Pulmonary oedema:** Radiologically confirmed, or oxygen saturation <92% on room air with respiratory rate >30/min, often with chest indrawing and crepitations on auscultation

**Significant bleeding:** Including recurrent or prolonged bleeding from nose, gums, or venipuncture sites; haematemesis or melaena

**Shock:** Compensated shock is defined as capillary refill  $\geq 3$  seconds or temperature gradient on leg (mid to proximal limb), but no hypotension. Decompensated shock is defined as systolic blood pressure < 70mm Hg in children or <80 mm HG in adults with evidence of impaired perfusion (cool peripheries or prolonged capillary refill)

**Hyperparasitemia:** *P. vivax* >2%

## Annex 7. Medications with Antimalarial Activity that Should not be Used During the Study Period

- ♣ Antimalarials: -Chloroquine, Amodiaquine; Quinine, quinidine; Mefloquine, halofantrine, lumefantrine; Artemisinin and its derivatives (artemether, arteether, artesunate, dihydroartemisinin); Proguanil, chlorproguanil, pyrimethamine; Sulfadoxine, sulfalene, sulfamethoxazole, dapsone; Primaquine; Aovaquone;
- ♣ **Antibiotics:** Tetracycline\*, Doxycycline, Erythromycin, Azithromycin, Clindamycin, Rifampicin, Trimethoprim, Pentamidine
- ◆ Tetracycline eye ointments can be used.

## ANNEX 8: Study Schedule

### Day 0:

---

#### Screening

- Clinical assessment including measurement of weight and height — referral in case of severe malaria/danger signs
- Measurement of axillary temperature
- Parasitological assessment
- Informed consent

- Pregnancy test, if indicated

#### Enrollment

- Treatment, first dose
- Blood sampling for blood smears, hemoglobin and filter paper

#### **Day 1:**

---

- Clinical assessment — referral in case of severe malaria/danger signs
- Measurement of axillary temperature
- Blood sampling for blood smears and filter paper
- Treatment, second dose or alternative treatment in case of early treatment failure

#### **Day 2:**

---

- Clinical assessment — referral in case of severe malaria/danger signs
- Measurement of axillary temperature
- Blood sampling for blood smears and filter paper
- Treatment, third dose or alternative treatment in case of early treatment failure

#### **Day 3, Day 7, Day 14, Day 21, Day 28, Day 35, and Day 42:**

---

- Clinical assessment — referral in case of severe malaria/danger signs
- Measurement of axillary temperature
- Blood sampling for blood smears and filter paper
- Alternative treatment in case of treatment failure
- Hemoglobin/hematocrit (Day 0, Day 14, Day 28, Day 42)

#### **Any other day:**

- Clinical assessment — referral in case of severe malaria/danger signs

- Measurement of axillary temperature
- Blood sampling for blood smears and filter paper
- Hemoglobin/hematocrit if indicated clinically
- Alternative treatment in case of treatment failure

## ANNEX 9: Schedule of Follow-Up Activities

	day 0	day 1	day 2	day 3	day 7	day 14	day 21	day 28	day 35	day 42	any other day
PROCEDURES											
Clinical assessment	X	X	X	X	X	X	X	X	X	X	X
Temperature	X	X	X	X	X	X	X	X	X	X	X
Blood slide for parasites count	X	X	X	X	X	X	X	X	X	X	X
Hemoglobin	X					X		X		X	X
Filter paper	X			X	X	(X)	(X)	(X)	(X)	(X)	X
Drug adverse event monitoring	X	X	X	X	X	X	X	X	X	X	X
TREATMENT											
Drug to be given	X	X	X								(X)
Rescue treatment		(X)	(X)	(X)	(X)	(X)	(X)	(X)	(X)	(X)	(X)

NOTES: Parentheses denote conditional or optional activities. Rescue treatment could be given on any day, provided that the patient meets the criteria for treatment failure. Extra days are any days other than regularly scheduled follow-up days when the patient returns to the facility because of recurrence of symptoms.

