## Rescue Treatment

Patients failing in any arm will be treated with second line drug per National Guidelines. Whereas, patients failing with the second line will be administered as of severe malaria criteria that is an indication of treatment failure.

The following are the known efficacy and adverse effects and pharmacokinetics of treatment drugs that will be used in the study:

**Chloroquine Plus Primaquine (CQ+PQ):** Chloroquine Plus Primaquine is a WHO Pre-qualified anti-malarial and FDA approved; WHO certifies the quality, safety and efficacy of the medication, and verifies that the manufacturer complies with WHO Good Manufacturing Practices. CQ+PQ is currently the first line anti-malarial recommended by Ethiopia FMOH for the treatment of uncomplicated falciparum infection. Adverse events are generally mild, most commonly GI (vomiting and diarrhea) and hematologic (anemia and eosinophilia). Its safety will be demonstrated in studies from Ethiopia and Uganda. Chloroquine has a half-life of 30-60 hours (53,54), while primaquine has a elimination half-life of 5-7 hours (54).

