### **Emergency Care**

Any patient with treatment failure or recrudescence will receive second line drugs. This will be given orally unless the patient has persistent vomiting, in which case it will be given Artesunate IM/IV until the vomiting resolves and then will be switched to oral therapy.

Patients with signs of severe malaria (altered mental status, coma, convulsions, hemoglobin <5g/dl, respiratory distress, circulatory collapse, or abnormal bleeding), persistent vomiting or

severe side effects will be hospitalized and receive parenteral therapy with artesunate and relevant supportive treatments, according to National Guidelines.

We will counsel patients and parents to return immediately if they or their child develops a raised rash (urticaria) or difficulty breathing suggestive of a severe allergic reaction. These patients will be treated with diphenhydramine or chlorpheniramine and will be withdrawn from the study. In addition, patient and or their parents, caretakers and family members will be counseled that the patient should not receive additional doses of the antimalarial they were given. These patients will be treated with oral quinine for seven days as per the rescue protocol.

Adult patients and parents with children in the study will be encouraged to return to the clinic for any fever or other signs of illness on any day during the 42-day follow-up period, allowing for early detection and treatment of illness before it becomes severe. Any hospitalization which occurs during the 42-day follow-up period will be paid by the study team.

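### Two treatment rules need reconciling: the adult haemoglobin limit for severe malaria differs between Emergency Care and Annex 6, and Annex 9 marks the study drug on recurrence visits without stating a condition

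*Combined protocol and SAP*

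**What the plan says.** **Severe malaria and haemoglobin.** Emergency Care opens its list with "Patients with signs of severe malaria (altered mental status, coma, convulsions, hemoglobin <5g/dl, respiratory distress" and sends these patients to hospital for parenteral therapy. It makes no age distinction and sets no parasite-count condition. Annex 6 gives <5 g/dl for children under 12 and a different adult limit: "<7g/dl and <20%, respectively, in adults) together with parasite count of" more than 10,000 (read here as per µl, since the unit is printed imperfectly).

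**Study drug on unscheduled days.** In Annex 9 the row "Drug to be given" has X on days 0, 1 and 2, nothing on days 3 to 42, and (X) in the last column, for any other day. The note explains that "Parentheses denote conditional or optional activities", and defines the column: "Extra days are any days other than regularly scheduled follow-up days when the patient returns to the facility because of recurrence of symptoms". Rescue treatment is a separate row with its own (X) in that column, and the note makes rescue depend on meeting the failure criteria. No condition is given for the study drug.

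Annex 8, for the same kind of visit, has one treatment entry: "Alternative treatment in case of treatment failure". The Rescue Treatment section says "Patients failing in any arm will be treated with second line drug per National Guidelines", and Emergency Care likewise gives second-line drugs after failure or recrudescence.

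**The concern.** For some adults the haemoglobin texts give two answers to whether the patient has severe malaria. Annex 6 is a definition and sets no treatment itself. It matters because Emergency Care ties parenteral therapy to severe malaria, the section on discontinuation and protocol violation withdraws patients with severe malaria on day 0 or progression to it, and Annex 4 uses severe malaria in early treatment failure and late clinical failure. One term with two meanings therefore affects a safety rule, who stays in the study and how an outcome is labelled.

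For the study drug, the Annex 9 cell can be read as letting staff give chloroquine plus primaquine again when symptoms recur. The plan has no analysis rule for that. The drug-related protocol violations cover only antimalarials from a third party or self-medication, so repeat dosing by study staff is neither a violation nor a censoring event.

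**Working it through.** **1. Haemoglobin rules side by side.** Emergency Care: severe if Hb <5. Annex 6, adults: severe anaemia if Hb <7 and count >10,000. The other signs in both lists, and the haematocrit alternative in Annex 6, are set aside. Test values:

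| Adult Hb (g/dl) | Parasites/µl | Emergency Care | Annex 6 |
|---|---|---|---|
| 4.5 | 5,000 | yes | no |
| 4.5 | 20,000 | yes | yes |
| 5.0 | 20,000 | no | yes |
| 6.0 | 5,000 | no | no |
| 6.0 | 20,000 | no | yes |
| 6.9 | 20,000 | no | yes |
| 7.0 | 20,000 | no | no |

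The rules disagree in two regions: (a) Hb 5 to <7 with count >10,000, severe only under Annex 6; (b) Hb <5 with count ≤10,000, severe only under Emergency Care. Elsewhere they agree.

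**2. Where the disagreement can act.**
- *Entry.* The Exclusion Criteria remove Hb <8, but Enrollment and Follow-up removes only Hb <5, and the screening form uses <5.0 and admits counts of 250 to 100,000/µl. An adult at Hb 6 with 20,000/µl is thus out under one section and in under the others. Once enrolled, that adult has severe malaria on day 0 if Annex 6 applies, which is an enrolment violation.
- *Days 1 to 3.* Haemoglobin is scheduled on days 0, 14, 28 and 42 only. An effect on early treatment failure needs an unscheduled measurement.
- *Days 14, 28 and 42.* Any parasitaemia from day 7 is already a failure under Annex 4. The Hb limit cannot move a patient between failure and adequate response at these visits. It can still decide the route of treatment, the label (late clinical or late parasitological failure in an afebrile patient), and whether the withdrawal rule for progression to severe malaria is triggered.

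**3. The Annex 9 cell.** The header has 12 cells and so does the study-drug row, so no column shift is visible; the (X) stands under any other day. Possible meanings:
- *Missed dose.* Not evident: non-attendance in the first 3 days leads to withdrawal.
- *Vomited dose.* Not evident: replacement follows vomiting within 60 minutes of dosing, hence on a dosing day.
- *Continuing primaquine.* Possible: Annex 5 gives it for 14 days, or weekly for 8 weeks, and the row marks only days 0 to 2. Against this, days 3 and 7 fall inside a 14-day course begun on day 0 and are blank, and the note ties the column to recurrent symptoms.
- *Repeat treatment.* Fits the column definition, but no text directs it, and it does not fit Annex 8, Rescue Treatment or Emergency Care if the patient has failed.

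The cell does not settle the question by itself.

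**The case against.** The strongest objection is that the Annex 9 point rests on one parenthesised cell. Rescue stands in its own row for the same day, so the table does not replace rescue with study drug, and the passages on second-line treatment concern patients who have already failed. That stands, and it limits the point to an ambiguity.

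A reader might go further and infer that re-dosed patients will have recurrences hidden and be counted as successes, lowering the failure rate. The documents do not support this. No text directs study drug for a returning patient, a blood slide is unconditional on such days, and parasitaemia with fever or a history of fever from day 4, or any parasitaemia from day 7, is already failure. A figure for the bias would need an assumed number of masked cases for which there is no basis.

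A reader might also see a conflict in the Emergency Care sentence on allergic reactions, "These patients will be treated with oral quinine for seven days as per the rescue protocol", because Rescue Treatment names no quinine. Rescue Treatment defers to national guidelines, which may be consistent with it, and the sentence concerns patients withdrawn from the study. No contradiction is shown.

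Finally, the haemoglobin difference might be thought to change early failure counts. With no haemoglobin planned on days 1 to 3, that is at most occasional. None of this removes the difference between the two severe-malaria criteria.

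**Conclusion.** The haemoglobin conflict is explicit. Its extent is the whole band of Hb 5 to <7 g/dl in adults with more than 10,000 parasites/µl, plus Hb <5 g/dl with 10,000 or fewer. How many patients fall there cannot be derived from the documents. The reason to correct it is that a safety rule and a term used for withdrawal and outcome have two meanings. No material shift in the failure rate has been shown.

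The Annex 9 inconsistency is real but softer: an entry without a condition, on days defined by recurrence, that Annex 8 omits and that does not fit the second-line rules if the patient has failed. This rests on the table having been read into the correct columns, which the cell count supports.

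**What to change.** 1. Reconcile Emergency Care and Annex 6 to one definition of severe malaria, covering both the adult haemoglobin limit and the parasite-count condition. Have the withdrawal rules and Annex 4 refer to it.
2. Reconcile the any-other-day study-drug cell in Annex 9 with Annex 8, Rescue Treatment and Emergency Care by stating what it covers and under what condition.
3. Add a sentence to Statistical Analysis on how a patient who receives study drug again after the planned course is handled: for example, censored on that date if no failure criterion has been met.

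Which haemoglobin limit and which drug apply is for the investigators and the national guideline to settle. The cost is wording in these sections and one analysis sentence, with no new visits, tests or patients.

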## **Annex 10: Consent Procedure**

### **Categories of consent forms**

- I. for children **6 months-11 years** old parental/guardian permission will be obtained
- II. For patients **12 -17 years old** assent from the patient and parental/guardian permission will be obtained
- III. For patients age **18 yrs. and older** adult consent will be obtained

### **Procedure**

1. Explain that he has P.vivax malaria infection and proceed with the consent process,
2. Read and Explain study objectives, procedures, the benefits and risks of taking part in the study.
3. If the person/guardian can read, provide a copy of the consent form in their preferred language and ask them to read the entire document. If they state that they cannot read, review the entire consent form with them using their stated preferred language version (Amharic/Afan Oromo). When finished, ask if they have questions.
4. Consenting participants and or their caretakers will be advised that they are free to decline any question or procedure and that they may terminate their participation at any time without loss of any benefits
5. If they agree to join the study get those to sign the consent form **with a witness (Obtain consent)**. Health worker/home visitor will act as a witness.
6. If the participant/guardian is illiterate, make a thumbprint using the left thumb by rolling the thumb from side to side on an inkpad and again on the consent form.
7. Once the consent form is completed, send it to the clinician to proceed
